3.1.3. Full Analysis Set Extension

The Full Analysis Set Extension (FAS-Ext) population will serve as the primary population for the analysis of efficacy data in this trial. Since the endpoints related to incontinence only apply to subjects who meet the definition of incontinence at trial entry, it is necessary to have a separate FAS definition with an additional criterion to define the primary analysis population for incontinence endpoints. Model-based estimates will be additionally restricted to only include subjects who were randomized to vibegron in the parent study.

The following FAS populations are defined in the study:

- **Full Analysis Set Extension (FAS-Ext):** All OAB subjects who took at least one dose of vibegron in the extension study and have at least one evaluable change from URO-901-3005 baseline micturition measurement in this study.
- **Full Analysis Set Extension for Incontinence (FAS-Ext-I):** All OAB subjects who took at least one dose of vibegron in the extension study, were included in the FAS-I population in the URO-901-3005 study, and have at least one evaluable change from baseline (i.e., Study URO-901-3005 baseline) urge urinary incontinence measurement in this study.

Subjects will be included in one of two vibegron treatment groups based on the original randomization from the parent study (URO-901-3005): 28 weeks Vibegron 75 mg, 52 weeks Vibegron 75 mg. Efficacy endpoints will be descriptively summarized by treatment group.

3.1.4. Per-Protocol Populations

The Per-Protocol Extension (PP-Ext) population and Per-Protocol Extension population for Incontinence (PPS-Ext-I) exclude patients from the FAS-Ext and FAS-Ext-I respectively due to important deviations from either protocol that may substantially affect the results of the efficacy endpoints (i.e., Major PDs associated with efficacy). Subjects assigned placebo in URO-901-3005 will only consider protocol deviations from URO-901-3006 and inclusion/exclusion protocol deviations from study URO-901-3005. The final determination of protocol violations, and thereby the composition of the Per-Protocol populations will be made prior to database lock and will be documented. A supportive analysis using the Per Protocol populations will be performed for the 6 secondary efficacy endpoints as defined in Section 1.1.2 (i.e., CFB in micturition, urgency, nocturia, and urge urinary incontinence episodes; IPSS Storage score; and volume voided per micturition).

Efficacy endpoints will be descriptively summarized by treatment group (i.e. 28 weeks Vibegron 75 mg, 52 weeks Vibegron 75 mg).

3.2. Violations and Deviation

Major protocol deviations are considered to have major impact on subject safety, efficacy or the validity of the study data.

Exclusion from per-protocol analysis is noted for each protocol deviation in the Protocol Deviation specifications. Patients with major protocol deviations that may impact efficacy results will be excluded from the PPS-Ext and PPS-Ext-I. Efficacy protocol deviations may include, but are not limited to the following:

- Subjects who do not meet the inclusion criteria
- Subjects who meet any of the exclusion criteria
- Concomitant use of prohibited medications
- Other (e.g., IP compliance < 70%)

Subjects excluded from the per protocol analysis in URO-901-3005 will also be excluded from per protocol analysis in URO-901-3006, with the exception of on-study protocol deviations in the placebo arm as noted in section 3.1.4.

The final list of major protocol deviations will be finalized and documented before database lock. All major protocol deviations related to efficacy will be discussed and finalized prior to database lock. Only major protocol deviations will be summarized and listed in the Clinical Study Report (CSR).

4. GENERAL STATISTICAL CONSIDERATIONS

4.1. General Principles for Data Analysis

4.1.1. Multicenter Study

In the parent study the stratified permuted block randomization is not done within centers. The analyses will be conducted by pooling data from all study centers and will not include study center as a covariate in the statistical modeling.

4.2. General Data Handling Conventions

4.2.1. Study Treatment Description

Treatment groups based on the randomized treatment in the parent study will be displayed as shown in the following table:

Table 1: Study Treatment Description

Data Displays for Reporting		
Description	Sections Included	Order in TLF
52 weeks Vibegron 75mg	Demographic and baseline data, Efficacy, Safety	1

28 weeks Vibegron 75mg	Demographic and baseline data, Efficacy (descriptive tables only), Safety	2
Overall Vibegron 75 mg	Demographic and baseline data, Safety	3

4.2.2. Reporting Conventions

General rules

In general, all collected safety data and any derived efficacy and PRO data will be presented in subject data listings for all enrolled subjects. This includes all data collected on the parent study, URO-901-3005, relevant to the definition of baseline and all data collected on URO-901-3005 after the first dose of vibegron, excluding assessments not repeated during 3006 (orthostatic vital signs, ECGs, urodynamics, and prostate volume measurement). Listings will be ordered by treatment group, subject number, and assessment week or event date. The treatment group presented in listings will be based on the actual treatment assignment in study URO-901-3005 (placebo as 28 Weeks Vibegron 75mg, vibegron 75mg as 52 weeks Vibegron 75mg), unless otherwise noted.

Summary tables will be provided for all subjects who sign informed consent for study URO-901-3006. Unless otherwise specified; all demographic and baseline data and safety data will be presented by treatment group and overall. Unless otherwise specified; all efficacy data will be presented by treatment group. In general, continuous variables will be summarized to indicate the population sample size (N), number of subjects with available data (n), arithmetic mean, SD, median, minimum, Q1, Q3 and maximum values. Categorical variables will be summarized by the population size (N), number of subjects with available data (n), number of subjects in each category, and the percentage of subjects in each category. Unless otherwise noted, the denominator to determine the percentage of subjects in each category will be based on the number of subjects with available data (n) in the analysis set of interest. Select ordinal data may be summarized using both descriptive statistics and counts and percentages of subjects in each category, as appropriate.

The data analyses will be conducted using the SAS[®] System (SAS Institute Inc., Cary, NC) version 9.4 or above. The eClinical Solutions standard operating procedures will be followed for the validation of all SAS programs and outputs.

Formats

Numeric data will be reported at the precision collected on the eCRF. The reported precision from non eCRF sources may be adjusted to a clinically interpretable number of decimal places.

Unscheduled Visits

Unscheduled visits will be assigned to a study visit using the all-inclusive windows defined in Section 4.2.4. However, data summaries for non-diary data will only report visits that are planned assessment time points for each parameter, according to the Time and Events table. All

visits for bladder diary data will be fully derived as described in section 4.2.4.2. Assessments at unscheduled visits will be included for “any time On-treatment” endpoints and in data listings.

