7.2. Subject Discontinuation/Withdrawal from the Study

- A subject who discontinues study drug will also be withdrawn from the study.
- A subject may choose to withdraw from the study at any time at his own request, or may be withdrawn at any time at the discretion of the investigator for safety, behavioral, compliance, or administrative reasons.
- If a subject withdraws consent for disclosure of future information, the Sponsor or designee may retain and continue to use any data collected before such a withdrawal of consent.
- If a subject withdraws from the study, he may request destruction of any blood or urine samples taken and not tested, and the investigator must document this in the site study records.
- Subjects who withdraw from the study will not be replaced.

The Week 52/Early Withdrawal assessments will be completed when a subject withdraws or is withdrawn from the study, if possible (see Schedule of Assessments in Section 1.3).

Reasons for discontinuation from the study include the following:

- AE
- Lack of efficacy
- Noncompliance
- Withdrawal of consent
- Lost to follow-up
- Physician decision
- Protocol deviation
- Death
- Other

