In general, continuous variables will be summarized by treatment to indicate the population sample size (N), number of subjects with available data (n), arithmetic mean, SD, median, Q1, Q3, minimum, and maximum values. Categorical variables will be summarized by N, n, number of subjects in each category, and the percentage of subjects in each category. Unless otherwise noted, the denominator to determine the percentage of subjects in each category will be based on the number of subjects with available data.

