1.2.4. Sample Size Justification

Approximately 300 subjects rolling over from Study URO-901-3005, in addition to other long-term safety data with vibegron, is sufficient to characterize the long-term safety profile of vibegron 75 mg once daily in men with symptoms of OAB on stable doses of pharmacological therapy for BPH. With the assumption of approximately 33% dropout, 100 subjects will be expected to complete the study for the duration of 1-year on vibegron.

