4.3.1.2. Exploratory Efficacy Endpoints (Bladder Diary)

4.3.2. Patient Reported Questionnaire Endpoints

4.3.2.1. International Prostate Symptom Score

The International Prostate Symptom Score (IPSS) is based on the responses to 7 questions concerning urinary symptoms and 1 question concerning quality of life. Each question concerning urinary symptoms allows the subject to choose 1 out of 6 answers indicating increasing severity of the particular symptom. The responses are assigned points from 0 to 5. The total score can therefore range from 0 to 35 (asymptomatic to very symptomatic).

The questions refer to the following urinary symptoms:

[figure not shown]
Questions	Symptom
1	Incomplete emptying
2	Frequency
3	Intermittency
4	Urgency
5	Weak Stream
6	Straining
7	Nocturia

[figure not shown]
Question 8 refers to the subject's perceived quality of life (QoL). The answers to the single question to assess the quality of life this question range from 0: "delighted" to 6: "terrible".

[figure not shown]
The IPSS questions reference storage symptoms (frequency, urgency and nocturia scores) and voiding symptoms (incomplete empty, intermittency, weak stream and straining) [1]. The following parameters will be derived:

CFB in IPSS storage score to Week 52 (secondary efficacy)

The IPSS storage score will be derived as the sum of the IPSS storage questions (sum of frequency, urgency and nocturia scores) for each visit. If any of these questions are not answered, the IPSS storage score will not be calculated.

Function Domain	Questions	Direction of Domain Scores

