14.2.3.3	Change from Baseline in Average Number of Nocturia Episodes per Day (MMRM)	PPS-Ext	Include all intervals, but present Week 52 first
14.2.4.1	Average Daily Number of Urge Urinary incontinence Episodes	FAS-Ext-I	Descriptive statistics, include CFB
14.2.4.2	Change from Baseline in Average Daily Number of Urge Urinary incontinence Episodes (MMRM)	FAS-Ext-I	Include all intervals, but present Week 52 first
14.2.4.3	Change from Baseline in Average Daily Number of Urge Urinary incontinence Episodes (MMRM)	PPS-Ext-I	Include all intervals, but present Week 52 first
14.2.5.1	International Prostate Symptom Score (IPSS) Storage Score	FAS-Ext	Descriptive statistics, include CFB
14.2.5.2	Change from Baseline in International Prostate Symptom Score (IPSS) Storage Score (MMRM)	FAS-Ext	Include all intervals, but present Week 52 first
14.2.5.3	Change from Baseline in International Prostate Symptom Score (IPSS) Storage Score (MMRM)	PPS-Ext	Include all intervals, but present Week 52 first
14.2.6.1	Average Volume Voided per Micturition	FAS-Ext	Descriptive statistics, include CFB
14.2.6.2	Change from Baseline in Average Volume Voided per Micturition (MMRM)	FAS-Ext	Include all intervals, but present Week 52 first
14.2.6.3	Change from Baseline in Average Volume Voided per Micturition (MMRM)	PPS-Ext	Include all intervals, but present Week 52 first
Other Efficacy and PROs Endpoints			

Title		Population	Programming notes
14.2.7.1	International Prostate Symptom Score (IPSS) Quality of Life Score	FAS-Ext	Descriptive statistics, include CFB
14.2.7.2	International Prostate Symptom Score (IPSS) Voiding Score	FAS-Ext	Descriptive statistics, include CFB
14.2.8.1	Urgency Episodes per Day 50% Responder Analysis	FAS-Ext	Descriptive statistics
14.2.9.1	Change from Baseline in Average Number of Total Incontinence Episodes per Day	FAS-Ext-I	Descriptive statistics, include CFB
14.2.9.2	Urge Urinary Incontinence Episodes per Day 75% Responder Analysis	FAS-Ext-I	Descriptive statistics
14.2.10.1	[REDACTED]	FAS-Ext	[REDACTED]
14.2.11.1	[REDACTED]	FAS-Ext	[REDACTED]
14.2.11.2	[REDACTED] Crosswalk Index Value	FAS-Ext	[REDACTED]
14.2.11.3	[REDACTED] VAS Value	FAS-Ext	[REDACTED]
14.2.12.1	Overall Symptom Severity Bladder Symptoms Based on [REDACTED]	FAS-Ext	[REDACTED]

Title		Population	Programming notes
14.2.12.2	Overall Symptom Control over Bladder Symptoms Based on [REDACTED]	FAS-Ext	Repeat 14.2.12.1
14.2.12.3	Overall Symptom Frequency Based on [REDACTED]	FAS-Ext	Repeat 14.2.12.1

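### Unless the blacked-out responder sections say otherwise, the 50% urgency and 75% UUI responder percentages leave out men without data at the visit and may overstate late response

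*SAP*

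**What the plan says.** SAP 4.2.2 sets the general rule that, unless an exception is noted, "the denominator to determine the percentage of subjects in each category will be based on the number of subjects with available data (n"). Protocol 9.4.1 has the same default. The same SAP paragraph requires categorical summaries to show N, n, the count in each category and the percentage.

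SAP Table 9 (11.1.1) lists two responder outputs under other efficacy and PRO endpoints: "Urgency Episodes per Day 50% Responder Analysis" (14.2.8.1, FAS-Ext) and "Urge Urinary Incontinence Episodes per Day 75% Responder Analysis" (14.2.9.2, FAS-Ext-I). The programming note for each says only that it is descriptive. It names neither a denominator nor a visit.

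SAP 4.3.4 sets percentage change to missing when the post-baseline value is missing. SAP 4.2.3 does not impute diary data for change from baseline, on the ground that an MMRM is used. It does not mention responder status.

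Under Protocol 7.2 a man who stops study drug is also withdrawn from the study, and "Lack of efficacy" is one of the listed reasons. The planned attrition is in SAP 1.2.4: "With the assumption of approximately 33% dropout, 100 subjects will be expected to complete the study".

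The places where the responder endpoints, their visits and any missing-data rule would be defined are SAP 1.1.3, 4.3.1.2 and 6.2.1. Their text is blacked out or absent in the public version, which is not a fault of the plan.

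**The concern.** A descriptive percentage has no model behind it, so the reason given for not imputing change from baseline does not carry over to responder status. Under the visible default, a man with no evaluable diary at a visit is not counted as a non-responder; he is removed from the denominator. If men who do poorly tend to leave, the rate at a late visit is the rate among those who stayed.

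The risk is one of reading. If the tables are laid out by visit, the percentage can rise over the extension with no change in any man, and that can be taken for growing long-term benefit. The secondary objective is worded as demonstrating long-term efficacy. The 28-week group gets only descriptive efficacy tables (SAP 4.2.1), so no model-based estimate stands beside its figures.

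**Working it through.** **Inputs**
- About 300 rollovers, 33% dropout, 100 men completing one year on vibegron: SAP 1.2.4.
- FAS-Ext needs one evaluable change from baseline in micturition during the extension: SAP 3.1.3. It can therefore include men with no Week 52 value.
- Diary windows: Week 28 is Days 187–207, Week 36 is Days 243–263, Week 52 is Days 345–385: SAP Table 3.
- Responder rates: the documents give none. Those below are assumptions.

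**1. The plan's own figure.** 300 × (1 − 0.33) = 201, which is not 100. With half of the rollovers coming from parent-study vibegron, 300 × 0.5 × 0.67 = 100.5, which matches. The half is an assumption; the extension documents do not state the split. On that reading 150 men start in the 52-week group and about 100 finish, so about 50 have no Week 52 value.

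**2. Who lacks a value.** A man who withdraws is asked for an early-withdrawal diary, but it counts as Week 52 only on Days 345–385. A diary from Days 208–242 or 264–344 falls in no window. A poor result can thus be recorded and still not enter a by-visit table. For non-diary data the Week 36 window ends at Day 308 and the Week 52 window opens after Day 309, so there is almost no such gap.

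**3. Formula.** Let *p* be the responder rate among men with data, *m* the share of the analysis set without data, and *r* the response of missing men relative to the others.

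- Rate over the whole analysis set = *p* × [(1 − *m*) + *m* × *r*]
- Overstatement = 1 / [(1 − *m*) + *m* × *r*]

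With *m* = 1/3 (50 of 150):
- *r* = 0: 1 / 0.667 = 1.50 (1 / 0.67 = 1.49 with the unrounded 33%)
- *r* = 0.5: 1 / (0.667 + 0.167) = 1.20
- *r* = 1: 1.00

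With *r* = 0, *m* = 20% gives 1 / 0.80 = 1.25 and *m* = 10% gives 1 / 0.90 = 1.11.

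**4. An observed rate of 60%, restated over the whole analysis set of 150**

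| Missing | None of the missing respond | Half as often | Equally often | All respond |
|---|---|---|---|---|
| 10% (135 seen) | 54.0% | 57.0% | 60.0% | 64.0% |
| 20% (120 seen) | 48.0% | 54.0% | 60.0% | 68.0% |
| 33% (100 seen) | 40.0% | 50.0% | 60.0% | 73.3% |

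At one third missing and no responders among the missing men, observed rates of 40%, 50% and 70% become 26.7%, 33.3% and 46.7%.

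**5. How a rate can rise with no change in any man.** Take 60 responders among 150 men, all of whom stay. The percentage over men with data is 60/135 = 44.4%, then 60/120 = 50.0%, then 60/100 = 60.0% as others leave. Over the full 150 it remains 40.0%.

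**The case against.** The strongest objection is that the default yields to any stated exception, and the sections where one would naturally sit cannot be read. This stands, and it makes the point conditional. On the other side, the visible table notes contain no exception, and the SAP states one openly where it wants one: in 5.2, percentages are taken over the analysis set.

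The table already has to show N, n and the count, so anyone can divide responders by N. This also stands. Attrition is disclosed, and the issue is which percentage is printed and how it is labelled.

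The direction is not known. Lack of efficacy is one of nine listed reasons, with no frequencies given. Men also leave for adverse events, for urinary retention or a high PVR, or miss visits because of COVID-19 (SAP 8). If missing men would have responded more often than the others, the observed rate would be too low.

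The 33% is planned dropout among rollovers. Men who leave before any evaluable extension diary are not in FAS-Ext at all, so the share of FAS-Ext missing at Week 52 may be smaller, and the 1.5 factor with it.

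Finally, the tables are exploratory, with no hypothesis or test, so no formal conclusion depends on them.

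**Conclusion.** The point holds in a conditional form. Under the visible default, and unless a blacked-out section says otherwise, both responder percentages are taken over men with data at the visit, and the late-visit rate may be too high. The size runs from no bias, if missing men respond equally, to 1.5-fold, if one third of the analysis set is missing and none of them responds. With 20% missing the corresponding figure is 1.25-fold. These figures rest on assumed response among missing men, and the one third also treats planned dropout as the share missing from FAS-Ext.

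A reader might infer that the Week 52 responder rate is inflated by about half, or that the SAP has no rule for missing responder status. The documents support neither. The first needs every missing man to be a non-responder and the full planned dropout to fall inside FAS-Ext. It also takes Week 52 as the responder visit, which no visible text states, although diary parameters are derived at every diary visit including Week 52 (SAP 4.3.1). The second treats blacked-out text as missing.

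**What to change.** For outputs 14.2.8.1 and 14.2.9.2:
- Keep the observed-case percentage and label it as men with data.
- Add a row with the FAS-Ext N (FAS-Ext-I N for UUI) as denominator, counting men without an evaluable value at the visit as non-responders.
- State in the SAP that this row is a sensitivity figure and an exception to the 4.2.2 default.

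The cost is one sentence and one extra row in each of two tables. The added figure will be less favourable, and it is conservative for men missing for unrelated reasons such as COVID-19; the observed-case row beside it covers that. It still describes FAS-Ext and not every treated man, because FAS-Ext requires one extension diary. If a blacked-out rule already provides this, no change is needed.

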4.2.3. Premature Withdrawal and Missing Data

All data collected in the study database after the subject’s cessation of study treatment should be included in summary and analysis as defined by analysis rules. Data of subjects who are not treated with vibegron on either Study URO-901-3005 or URO-901-3006 will only be listed.

If any missing data are present in diary data for any reasons, no explicit missing data imputation will be performed for the analysis of change from baseline since a mixed model for repeated measures (MMRM) will be applied to change from baseline analysis.

Missing items from the subject reported outcomes (PROs) will not be imputed. Some scores may still be calculated from the non-missing questions; handling rules are detailed for each individual PRO within the appropriate subsection of 4.3.2.

In general, missing safety data will not be imputed and only observed values will be analyzed.

If the relationship of an AE record (“Relationship to investigational product” on AE CRF) is missing this AE will be considered “Probably Related” to the study treatment. If the AE intensity is missing every effort should be made to acquire the information from the investigator. “Severe” will be assigned to a missing intensity for reporting purposes.

Dates of AEs and medications reported under the URO-901-3005 protocol (including all start dates of events and medications initially reported in URO-901-3005 and end dates of events and medications that were not ongoing at the time of URO-901-3006 entry) will follow the date imputation rules from the URO-901-3005 SAP; dates will not be re-imputed.

The general imputation rules of partial missing date and time for both AE and medication is detailed below:

Dates missing the day of the year will adhere to the following conventions:

- The missing day of onset date will be set to:
 - The day of first active treatment with vibegron in URO-901-3006, if the onset YYYY-MM is the same as YYYY-MM of the first active treatment
 - First day of the month that the event occurred otherwise.

- The missing day of end date will be set to:
 - The death date, if the end date YYYY-MM is the same as the YYYY-MM of the death date
 - The end of study participation, if the end date YYYY-MM is the same as the YYYY-MM of the end of study participation date
 - The last day of the month of the occurrence otherwise.

Dates missing both the day and month of the year will adhere to the following conventions:

- Missing onset date will be set to:
 - January 1 of the year of the onset, if the onset YYYY is after the YYYY of the first active treatment
 - The date of the first active treatment in URO-901-3006, if the onset YYYY is the same as the YYYY of the first active treatment

- The missing end date will be set to:
 - The death date, if the end date YYYY is the same as the YYYY of the death date
 - The end of study participation, if the end date YYYY is the same as the YYYY of the end of study participation date
 - December 31 of the year of occurrence otherwise.

